9.0 Statistical Considerations

This is a partially blinded, randomized study to evaluate the effects of intervention upon Ki-67 and other biomarkers. Participants and researchers will be blinded with regard to assignment of study drug (placebo vs. metformin) but they will not be blinded with regard to assignment of lifestyle intervention. We will use a form of adaptive randomization called minimization, which is similar to stratification in that participant characteristics are used to assign them to the treatment conditions to achieve better group balance. Groups will be balanced with regard to age (50-65 years), BMI (Class I and II: 30.0-39.9 and Class III or greater: ≥ 40), and whether they meet current exercise guidelines as recommended by the Physical Activity Guidelines for Americans.

The primary objective of this study is to evaluate the effect of intervention (metformin and/or lifestyle intervention) on Ki-67. Secondary endpoints include examination of intervention on:

- (a) genes relevant to estrogen dependent endometrial proliferation, hyperplasia and cancer using Q-PCR (PCNA, sFRP4, RALDH2, IGF-1R, survivin, and EIG121),
- (b) biomarkers specific to the effect of metformin treatment (phospho-AMPKa, phospho-ACC, phospho-mTOR and phospho-S6 ribosomal protein).

Additionally, we will examine changes in serum levels of estradiol, estrone, testosterone, DHEA-S, sex hormone binding globulin (SHBG), adiponectin, glucose,

HbA1c, insulin and insulin-like growth factor-1 (IGF-1) and all biobehavioral outcomes, such as changes in body composition, physical activity, quality of life (QoL), diet, etc.

We will analyze differences in Ki-67 and other outcomes using 2x2 ANOVA models. If lifestyle intervention is found to affect change in Ki-67 expression or other outcomes, we will use the methods described by Baron and Kenney [78] to determine whether these changes were mediated by weight loss, body composition changes, physical activity changes, and dietary changes. Differences between arms with regard to adverse events and other toxicities will be examined using Fisher's exact tests. Changes from baseline lab values will be examined 2x2 ANOVA models.

A study of Ki-67 change in participants at high risk for endometrial cancer (Lynch patients) indicated we could expect a mean decrease in Ki-67 of 3.5 (after log-transformation) in the Metformin alone group with a standard deviation of 0.8. For the purposes of estimating power, we assumed that the lifestyle intervention alone group would have the same mean and standard deviation decrease, but we halved mean decrease for our calculations to take into account the non-compliance we might observe in this group. Finally, we estimated power for a moderate interaction effect – half of the metformin intervention effect in addition to the additive effect of metformin and lifestyle intervention. Specifically, we calculated power assuming that the mean decreases in the control arm, metformin alone arm, lifestyle intervention alone arm and metformin plus lifestyle intervention arm were 0, 3.5, 1.75 and 7, respectively. Using a 2-sided test with 5% statistical significance, we will have over 95% power to detect these differences when the common standard deviation is 0.8. Additionally, we will still have adequate power to detect much smaller differences. For example, we will have 80% power to detect a lifestyle alone main effect of 0.3 and still have over 95% power to detect a metformin main effect and an interaction effect of 0.6 and 1.2, respectively, when the common standard deviation is 0.8. Power was calculated using PASS 2005 (copyright

© 2005, Jerry Hintze).

All testing will be 2-sided with 5% statistical significance. The primary efficacy analysis will be intent-to-treat. Patients who discontinue early from the study will be included in the analysis as not having a change from baseline values. Additionally, we will use the methods described by Benjamini and Hochberg [51] to control the false discovery rate in the secondary efficacy analyses.

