1.2 Endpoints

1.2.1 The primary endpoint biomarker that will be investigated is proliferation Ki-67.

1.2.2 Secondary endpoints include:

1.2.2.1 Changes in serum levels of estradiol, estrone, testosterone, DHEA-S, sex hormone binding globulin (SHBG), adiponectin, glucose (fasting), HbA1c, insulin (fasting) and insulin-like growth factor-1 (IGF-1).

1.2.2.2 Changes in diet, physical activity, body composition (BMI, waist and hip circumference, and measurements from the DEXA scan), quality of life, and psychosocial determinants of behavior change will be examined in this sample of obese, post-menopausal women taking metformin or receiving a diet and physical activity intervention.

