The Ki-67 as well as the biomarkers associated with metformin action analysis will be performed by the MD Anderson Core Histology lab and read by [name] in the Pathology Core. Q-PCR analyses will be performed by [name], PI of the Biomarkers core. [name] has been interested in identifying genes in human endometrium whose expression is altered by hormone replacement therapy (HRT). Over the last 5 years he has used several techniques including differential display, microchip array screening, and real-time quantitative PCR to find such genes. The tools he has developed are directly applicable to the investigation of surrogate endpoint biomarkers (SEBs) in HNPCC patients treated with estrogens or estrogens plus

progestins.

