- a) randomized to one of the four intervention groups using the Department of Biostatistics Clinical Trial Conduct Website. See section 7.0 for details.
- b) given prescription to fill the study medication at the pharmacy at MD Anderson Cancer Center.
- c) participant will be provided education on recording and monitoring daily intake of study medication into the Pill Diary. See Appendix M for Pill Diary.

- d) review and report side effects of the study medication.

Once the participant is randomized, the research nurse will notify the pharmacist to inform them of the randomization code in order to keep study staff blinded to assignment to metformin vs. placebo.

In-person toxicity assessments will be performed at the end of the first, second, third, and fourth month (plus or minus 10 days). Phone assessments will be done periodically as needed to assess for adverse effects. At the end of the fourth month of the study, the participant will return for the **Post-Treatment Evaluation** to repeat all measurements (all blood tests, anthropometric assessments, second biopsy, and survey packet) taken at the Screening Visits (1& 2). The participant will also be given a Satisfaction Questionnaire, based on their intervention, in advance to complete and return at this visit.

One year after baseline (+/- 1 month), participants will be contacted to complete a 1 Year Follow-Up Evaluation. This evaluation will include anthropometrics assessments, including a DEXA scan, the survey packet, and blood tests collected from the 4th month visit (see Table 5: Study Parameters for the list of laboratory test to be collected for 1 year Follow-up Evaluation). During this visit, the participant will also be compensated with a parking voucher to cover the cost of parking during the visit.

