6.1 Treatment

Prior to beginning therapy, participants will have a baseline endometrial biopsy performed. If the baseline endometrial biopsy reveals endometrial hyperplasia or cancer or if an office endometrial biopsy cannot be performed the participant will be removed from study. Women with abnormal biopsy results will be referred to contact their Gynecologist from their insurance provider for further treatment for these results.

The study is partially blinded in that investigator and participants will be blinded to the treatment of Metformin versus placebo, but will be un-blinded in regard to the lifestyle intervention. All participants will be followed for at least one month after their last dose of study medication. All treatment-related toxicities will be followed by phone until resolution. All other participants will be randomized to one of four arms:

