7.0 Data Monitoring Plan

Participants will be randomized to one of the four arms: metformin, placebo, and metformin / placebo and lifestyle intervention using the Department of Biostatistics Clinical Trial Conduct Website (CTC website). Participants who do not meet these criteria will be considered nonevaluable, removed from study and will not be counted toward the actual accrual goal. We plan to accrue 100 evaluable participants.

We will use a form of adaptive randomization called minimization, which is similar to stratification in that participant characteristics are used to assign them to the treatment conditions [75, 76]. Minimization results in better group balance with respect to participant characteristics. In minimization, before a participant is assigned to a treatment group, the total numbers of participants in each group with similar covariate characteristics are totaled. The totals are based on the marginal sums of the covariates so that each covariate is considered separately. The treatment assignment of a participant is determined based on which group would provide the best overall balance with respect to those covariates. Covariates that will be used in randomization of participants in this study are BMI, age, and whether the participant meets current guidelines for exercise recommended by the Physical Activity Guidelines for Americans. These guidelines recommend that adults engage in moderate physical activity at least 150 minutes per week or in vigorous activity 75 minutes per week [77]. The baseline level of activity for each participant will be measured when they complete the Godin questionnaire, which is part of their survey packet, which will be completed before their Screening Visit 2 appointment. The Research Dietitian/Research Coordinator will determine if the participant is currently meeting these recommendations and provide

this data to the Research Nurse for randomization.

Randomization will be performed by the research nurse using the website created by the Department of Biostatistics. The research nurse will then inform the pharmacist of randomization group (A, B, C, or D) for study drug administration. The Research Dietitian/Research Coordinator who is in charge of administering the lifestyle intervention will be given access to the randomization website and informed of lifestyle intervention randomization code to determine whether the participant has been randomized to the lifestyle intervention.

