12.6 Immunohistochemistry

Ki-67 immunohistochemistry and phospho-AMPKa, phospho-ACC, phospho-mTOR and phospho-S6 ribosomal protein will be performed in the Histology Core Lab, using paraffin-embedded tissue sections and commercially available antibodies. The percentage cells positive will be recorded, as well as the compartment stained (epithelial cell vs. stromal cell); nucleus vs. cytoplasm vs. cell membrane). [name] will evaluate the immunohistochemistry slides.

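### The plan does not require the person who scores Ki-67 to be masked to lifestyle arm, so it permits unmasked reading of the primary endpoint for the lifestyle main effect

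*Combined protocol and SAP*

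**What the plan says.** The blinding rule appears twice. Section 6.1 states that "investigator and participants will be blinded to the treatment of Metformin versus placebo, but will be un-blinded in regard to the lifestyle intervention". Section 9.0 applies the same rule to participants and researchers: they are blinded to study drug, "but they will not be blinded with regard to assignment of lifestyle intervention". The masking step at randomization in Section 5.4 concerns the drug only: the pharmacist is told the code "in order to keep study staff blinded to assignment to metformin vs. placebo". Section 7.0 has the Research Dietitian/Research Coordinator "informed of lifestyle intervention randomization code to determine whether the participant has been randomized to the lifestyle intervention". It does not mention the slide reader.

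On the endpoint, Section 1.2.1 says: "The primary endpoint biomarker that will be investigated is proliferation Ki-67". Section 2.6 says that the Ki-67 "analysis will be performed by the MD Anderson Core Histology lab and read by" a named person in the Pathology Core. Section 12.6 describes the score: "The percentage cells positive will be recorded, as well as the compartment stained". A named person "will evaluate the immunohistochemistry slides". Section 11.1.2 has the biopsy slides reviewed centrally by the study's co-PI, who is also PI of the Pathology Core. The names themselves have been removed from the public text.

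**The concern.** An open lifestyle arm is unavoidable for participants and for the staff who deliver the sessions. It is not unavoidable for someone reading a slide. Counting positive cells involves judgement, and Section 12.6 gives no number of cells to count, no rule for choosing fields and no second reader for the immunohistochemistry. Masking is the natural safeguard, and it is not written down.

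At stake is the lifestyle main effect on Ki-67. If post-treatment slides from lifestyle participants were read lower, the analysis could not afterwards separate that from a real effect. The risk matters most if the true effect is zero or small. A false lifestyle finding would also trigger the mediation analyses planned in Section 9.0.

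**Working it through.** **Setting the text side by side**

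| Question | Where | Answer |
|---|---|---|
| Who is unblinded to lifestyle? | 6.1, 9.0 | Investigator, researchers, participants |
| Is there an exception for outcome readers? | 6.1, 9.0 | None stated |
| What does the masking step at randomization cover? | 5.4 | Metformin versus placebo only |
| Who is given the lifestyle code? | 7.0 | Dietitian/coordinator; the reader is neither given it nor denied it |
| Who scores Ki-67? | 2.6, 12.6 | A person in the Pathology Core |
| Who heads that core? | 11.1.2 | The study's co-PI |
| Are coded slides or a masked reader required? | 2.6, 11.1, 11.2, 11.4.1, 11.4.2, 12.6 | Not in any of these |

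The head of the Pathology Core, as co-PI, plausibly falls within the investigators and researchers whom the rule leaves unblinded to lifestyle. Nothing in the sections on slide handling or reading takes the Ki-67 reader out of that group. Following the plan to the letter therefore allows an unmasked read.

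**Which contrasts are exposed**

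Write C, M, L and ML for the mean decreases in the control, metformin, lifestyle and combined arms. Let a constant reading shift s be added to L and ML.

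- Lifestyle main effect: [(L − C) + (ML − M)]/2 changes by (s + s)/2 = s.
- Metformin main effect: [(M − C) + (ML − L)]/2 changes by (0 + s − s)/2 = 0.
- Interaction: ML − M − L + C changes by s − s = 0.

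Only the lifestyle main effect moves.

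**Scale, for illustration only**

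Inputs from Sections 5.4 and 9.0: 25 per arm, SD 0.8 after log transformation, two-sided 5%, planned mean decreases 0, 3.5, 1.75 and 7.

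- Planned lifestyle main effect: [(1.75 − 0) + (7 − 3.5)]/2 = 2.625.
- Standard error, 50 versus 50: 0.8 × √(2/50) = 0.16.
- The planned effect is 2.625/0.16 = 16.4 standard errors. Power is over 99.9%, which agrees with the plan's statement of over 95%.

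The documents give neither a misreading size nor the base of the logarithm. Assume that lifestyle post-treatment slides are read a relative 10% low. The shift is then −log(0.9). With no true effect, the rejection rate comes from a noncentral F with 1 and 96 degrees of freedom and noncentrality (shift/0.16)².

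| Log base | Shift | Share of 2.625 | False-positive rate |
|---|---|---|---|
| 10 | 0.046 | 2% | 5.9% |
| e | 0.105 | 4% | 10.0% |
| 2 | 0.152 | 6% | 15.6% |

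The shift is small against the planned effect. It is not negligible against a 5% error rate when there is no effect.

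**The case against.** The strongest reply is that the documents never show the reader learning the arm. Section 7.0 gives the lifestyle code to the dietitian/coordinator, and the list in Section 7.2 of what PDMS and CORe hold does not include lifestyle allocation. Baseline biopsies are reviewed for diagnosis before randomization, so at that point there is no arm to know. Laboratories may also mask as routine. All of this makes unmasking less likely, and it limits the point to what the plan permits. It does not supply the missing requirement: Section 7.0 does not withhold the code from the reader, and no section describes routine masking.

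Two stronger readings are tempting, and neither is supported. First, a reader might infer that the co-PI who reviews the biopsies for diagnosis also scores Ki-67 and knows the lifestyle arm. The names are removed, so whether the two are one person cannot be determined from this text. Shared tissue blocks and a pathology report sent to the study gynecologist may make a slide traceable to a participant, but they do not reveal her arm to the reader.

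Second, a reader might set the illustrative shift against 1.75 or 0.3 and get larger shares. The figure 1.75 is the planned decrease in one arm, not the main effect being tested. Section 9.0 calls 0.3 a main effect with 80% power, but a main effect of 0.3 has about 46% power. Power of about 80% is recovered if 0, 0.6, 0.3 and 1.2 are taken as arm means, and the lifestyle main effect is then [(0.3 − 0) + (1.2 − 0.6)]/2 = 0.45. That ambiguity is a separate matter and should not be used to enlarge this one.

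**Conclusion.** The point holds as a gap in the written plan. Investigators and researchers are expressly unblinded to lifestyle, outcome readers are not excepted, and the primary endpoint is scored by a person with no requirement for coded slides or masking. Unmasked reading is permitted for one of the two effects in the primary objective; it is not shown to occur.

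The reach is narrow. The metformin contrast is covered by the drug blinding, provided the reader counts as a researcher under Section 9.0, and a constant shift on lifestyle slides cancels from the metformin and interaction contrasts. No size for the bias can be taken from the documents. The 6% to 16% range rests on an assumed 10% misreading in one direction and on the log base, and the conclusion does not depend on it. The change should be made because it closes a route to bias in the primary endpoint at little cost. The gap does not by itself invalidate the trial.

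**What to change.** In Section 12.6 add: *Ki-67 and phospho-IHC slides are labelled with a code only; the reader does not have the code list or the lifestyle or drug allocation until the readings are locked.* In Sections 6.1 and 9.0 state that the IHC reader is an exception to the lifestyle unblinding.

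The cost is relabelling the IHC slides and a code list kept by someone other than the reader. A link between code and participant still exists, so readings can be paired; the reader simply does not hold it. Diagnostic review and its report are unchanged, and no visit, procedure or tissue is added. If the laboratory already works this way, the change only records it.

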5.3.1 Endometrial biopsy

An endometrial pipelle biopsy will be performed at the Screening Visit 2 and at the 4th month on days 115-125 (plus or minus 10 days) into treatment in all participants from (all four arms) both groups.

In addition to histologic examination, each endometrial biopsy will be examined for proliferation markers as well as other biomarkers. The second biopsy in the no treatment group is important in order to determine variability in the biomarkers due to sampling. In preliminary data from the Wyeth-Ayerst Study, we did see variability in certain transcript levels at the 3 and 6 month time points even in the placebo control group. Therefore, we feel strongly in this study that women in both groups undergo a 4 month EMB.

Risks of office endometrial biopsy are small, and while there are no published data on risk of perforation, we believe that the risk is less than 1/1000. Even in those participants in whom uterine perforation occurs, observation alone is usually sufficient. The severe perforations requiring laparotomy and emergent hysterectomy are not seen in office endometrial biopsies, rather in Dilatation and Curettage (D & C) procedures performed in the operating room.

Participants who have no allergies will be instructed to take orally Non- Steroidal Anti-inflammatory Drugs (NSAIDs) before and after the biopsies to reduce pain and cramping. The NSAIDs medications are available over the counter (See Section 5.2 for the recommended dose).

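### The 2x2 ANOVA appears to use baseline only by subtraction and leaves out the three minimization factors; a pre-specified ANCOVA would cost little and usually be more precise

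*Combined protocol and SAP*

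**What the plan says.** Section 9.0 gives one model for the continuous outcomes: "We will analyze differences in Ki-67 and other outcomes using 2x2 ANOVA models". For laboratory values it adds: "Changes from baseline lab values will be examined 2x2 ANOVA models". No covariate is named in either sentence or anywhere else in the analysis plan.

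For Ki-67 the sentence does not say outright that the analysed variable is change. Three other features of Section 9.0 point that way:

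- The mediation analysis is conditional on lifestyle affecting change in Ki-67.
- The power calculation is built on mean decreases.
- The rule for early discontinuation reads: "Patients who discontinue early from the study will be included in the analysis as not having a change from baseline values".

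Allocation is by minimization. Section 7.0 states: "Covariates that will be used in randomization of participants in this study are BMI, age, and whether the participant meets current guidelines". Section 9.0 repeats the factors: "Groups will be balanced with regard to age (50-65 years), BMI (Class I and II: 30.0-39.9", with a second BMI class of 40 or above, and exercise-guideline status. The only age level given, 50-65, is the whole eligible range.

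On available data, Section 5.4 has participants return at the end of month 4 "to repeat all measurements (all blood tests, anthropometric assessments, second biopsy, and survey packet) taken at the Screening Visits". Section 5.3.1 says of earlier data: "we did see variability in certain transcript levels at the 3 and 6 month time points even in the placebo control group".

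**The concern.** Subtracting baseline is a regression on baseline with the slope forced to 1. If the true slope is below 1, as it is when repeated measurements are imperfectly correlated and have similar spread, subtraction over-corrects and leaves avoidable noise in the outcome. ANCOVA estimates the slope instead.

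Leaving out the minimization factors raises a second point. Minimization balances the arms on these factors, but the unadjusted error term still contains whatever variance they explain. If they predict the outcome, the standard error is too large and the test is conservative. The documents do not say whether they do.

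At stake is the precision available for smaller Ki-67 effects, which Section 9.0 claims to cover, and for the many secondary continuous outcomes. The latter have no stated power and are subject to false discovery rate control. Adverse events, compared by Fisher's exact test, are unaffected.

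**Working it through.** **Inputs from the documents.** 25 women per arm, 100 in total (Sections 5.4 and 7.0); SD 0.8 for the decrease in log Ki-67, and two-sided 5% tests (Section 9.0). The correlation r between baseline and month 4, the SD ratio k = SD(month 4)/SD(baseline), the dropout rate and the variance explained by the factors are not given. All values of these below are assumptions.

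**1. The plan's own power figures.** The averaged main effect has SE = 0.8 × √(1/50 + 1/50) = 0.16. The interaction contrast has SE = 0.8 × √(4/25) = 0.32. Error df = 100 − 4 = 96.

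- Planning means 0, 3.5, 1.75, 7: the interaction contrast is 7 − 3.5 − 1.75 + 0 = 1.75, giving 99.97% power. The main effects (4.375 and 2.625) have more. The stated figure of over 95% is reproduced.
- Smaller effects: the plan says "For example, we will have 80% power to detect a lifestyle alone main effect of 0.3" and claims over 95% for a metformin effect of 0.6 and an interaction of 1.2.
  - Read as arm means 0, 0.6, 0.3, 1.2: the lifestyle effect is (0.3 + 1.2)/2 − (0 + 0.6)/2 = 0.45, power 79.5%. The metformin effect is 0.75, power 99.6%. The interaction contrast is 0.3, power 15.3%.
  - Read as contrasts: 0.3 has 45.9%, while 0.6 and 1.2 each have 96.0%.
  - Each reading reproduces two of the three stated figures. The detectable effects below do not depend on which is right.

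**2. Precision of the planned test.** 80% power is reached at an averaged main effect of 0.453 and an interaction contrast of 2 × 0.453 = 0.906.

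**3. Gain from estimating the baseline slope.** The variance ratio, ANCOVA to change score, is k²(1 − r²)/(1 + k² − 2rk). With k = 1 this is (1 + r)/2. Estimating four covariates multiplies the variance by 95/91 = 1.044 and leaves 92 df. The factors are credited here with no explained variance.

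| r (k = 1) | Variance ratio | Detectable main effect | Detectable interaction | Power at 0.45 |
|---|---|---|---|---|
| Planned ANOVA | 1 | 0.453 | 0.906 | 79.5% |
| 0.3 | 0.65 | 0.373 | 0.746 | 92.2% |
| 0.5 | 0.75 | 0.401 | 0.802 | 88.2% |
| 0.7 | 0.85 | 0.427 | 0.853 | 84.0% |
| 0.9 | 0.95 | 0.451 | 0.902 | 79.8% |
| Any r and k with r × k = 1 | 1 | 0.463 | 0.926 | 77.8% |

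At r = 0.5, about 100 × 0.75 × 1.044 = 78 women would give the precision that the planned ANOVA gets from 100.

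**4. Unequal spread.** At r = 0.5 the ratio is 0.571, 0.75, 0.893 and 1.000 for k = 0.8, 1, 1.25 and 2. The gain disappears when r × k = 1, because subtraction is then the right slope.

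**5. The no-change rule.** If a fraction d of women have change set to zero, the proportional gain g becomes (1 − d) × g. At r = 0.5 and k = 1, 25% falls to 22.5% with 10% dropout and to 20% with 20% dropout.

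**6. The minimization factors.** Four-arm minimization was simulated with assumed prevalences (40% in the higher BMI class, 30% meeting exercise guidelines) and an assumed age split at 57.5. The unadjusted test's type I error was about 4.9%, 4.5% and 2.5% when the factors explained 0%, 7% and 26% of the variance. The adjusted test stayed at 4.9-5.0%.

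**The case against.** The strongest reply is that this is a preference and not a defect. The planned analysis is unbiased, keeps its error rate and has ample power at the planning means. That is correct.

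The benefit also depends on quantities that the documents do not give. The variability noted in Section 5.3.1 concerns certain transcripts in another study, not Ki-67, and comes with no correlation. It makes r below 1 plausible for some markers and supports nothing more exact.

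The 0.45 illustration lies where a power curve is steep. If 0.3 is meant as an averaged effect, ANCOVA does not rescue it: power goes from 45.9% to 61.5%, 55.4%, 50.4% and 46.1% at r = 0.3, 0.5, 0.7 and 0.9. The inconsistency in the smaller-effect power figures is a separate matter and adds no weight here.

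The case for the three factors is weaker than the case for baseline. If they predict nothing, a baseline-only ANCOVA is slightly better: 89.2% against 88.2% at r = 0.5 and an effect of 0.45. For activity and body composition, exercise status and BMI class partly repeat the outcome's own baseline. Against this, adjusting for the factors used in allocation protects against a conservative test and costs about one point of power.

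Two further limits stand. Every power figure uses the Ki-67 SD, so the gain for secondary outcomes is not quantified. Some Q-PCR baselines may also be missing, since Section 12.1 reports enough RNA in 87% of untreated post-menopausal women; a change score has the same problem.

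**Conclusion.** The concern holds as a low-cost improvement and not as an error in the plan. No analysis uses the baseline value as a covariate or includes the minimization factors.

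With SD 0.8 and equal SDs at both times, power at an effect of 0.45 rises by about 4 to 13 points for r between 0.7 and 0.3, and by almost nothing at r = 0.9. The worst case shown, r × k = 1 with uninformative factors, loses under two points (79.5% to 77.8%). That ANCOVA is usually more precise is therefore well founded; by how much in this trial cannot be read from the documents.

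The change-score reading for Ki-67 is an inference, though a well-supported one. If month-4 values alone were analysed, baseline would not be used at all and the case for adjustment would remain. Confidence is medium because r, k, dropout and the factors' explained variance are all assumed.

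**What to change.** In Section 9.0, make the primary model an ANCOVA of month-4 log Ki-67 on metformin, lifestyle, their interaction, baseline log Ki-67, BMI class (30.0-39.9; 40 or above), age as a continuous covariate, and exercise-guideline status (yes/no). Use the same form, with each outcome's own baseline, for the Q-PCR, phospho-protein, serum, body composition, diet, activity and quality-of-life outcomes. Fix the covariates and their coding before analysis.

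If the no-change rule for discontinuation is kept, state that it means setting the month-4 value equal to baseline. Keep the unadjusted 2x2 ANOVA of change as a sensitivity analysis.

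The cost is SAP wording and four error degrees of freedom (96 to 92). No new data are needed.
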